1.2.2 Clinical studies with AUSTEDO

Double-Blind, Placebo-Controlled Study – Chorea associated with HD

The efficacy of AUSTEDO as a treatment for chorea associated with Huntington's disease was established primarily in Study 1, a randomized, double-blind, placebo-controlled, multi-center trial conducted in 90 ambulatory subjects with manifest chorea associated with Huntington's disease. The diagnosis of Huntington's disease was based on family history, neurological exam, and genetic testing. Treatment duration was 12 weeks, including an 8-week dose titration period and a 4-week maintenance period, followed by a 1-week washout. Subjects were not blinded to discontinuation. AUSTEDO was started at 6 mg per day and titrated upward, at weekly intervals, in 6 mg increments until satisfactory treatment of chorea was achieved, intolerable side effects occurred, or until a maximal dose of 48 mg per day was reached. The primary efficacy endpoint was the Total Maximal Chorea Score, an item of the Unified Huntington's Disease Rating Scale (UHDRS). On this Scale, chorea is rated from 0 to 4 (with 0 representing no chorea) for 7 different parts of the body. The total score ranges from 0 to 28. Of the 90 subjects enrolled, 87 subjects completed the study. The mean age was 54 (range 23 to 74). Subjects were 56% male and 92% Caucasian. The mean dose after titration was 40 mg per day. Total Maximal Chorea Scores for subjects receiving AUSTEDO improved by approximately 4.4 units from baseline to the maintenance period (average of Week 9 and Week 12), compared to approximately 1.9 units in the placebo group. The treatment effect of -2.5 units was statistically significant (p<0.0001). The Maintenance Endpoint is the mean of the Total Maximal Chorea Scores for the Week 9 and Week 12 Visits. At the Week 13 follow-up Visit (1 week after discontinuation of the study medication), the Total Maximal Chorea Scores of subjects who had received AUSTEDO returned to baseline. A patient-rated global impression of change assessed how subjects rated their overall Huntington's disease symptoms. Fifty-one percent of subjects treated with AUSTEDO rated their symptoms as "Much Improved" or "Very Much Improved" at the end of treatment, compared to 20% of placebo-treated subjects. In a physicianrated clinical global impression of change, 42% percent of subjects treated with AUSTEDO rated their symptoms as "Much Improved" or "Very Much Improved" at the end of treatment compared to 13% of placebo-treated subjects.³

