2.3 Safety Outcome Assessments

The following assessments will establish the safety and tolerability of AUSTEDO during the AUDYT trial:

- Tolerability will be established by the proportion of study subjects able to titrate up to 48 mg/d (or up to 36 mg/d if receiving a strong CYP2D6 inhibitor) and able to complete the study at this dosage.
- Adverse events will be surveyed during all study Visits and during weekly telephone communications with the study subjects that will happen during the ramp-up period.
- AUSTEDO may prolong the QT interval. QT interval prolongation is associated with the development of tachyarrhythmias and Torsades de Pointes. To screen for the development of significant QT prolongation (defined as a corrected QT –Bazett– interval of 450 (458) milliseconds –or higher– in men or 460 (472) milliseconds –or higher– in women), a 12-lead electrocardiogram (ECG) will be performed during all scheduled study Visits, including the early termination Visit, if such a Visit happens. Should there be evidence of QT prolongation, it will remain at the investigator's discretion whether to discontinue the study drug, or to reduce the dose to a new, maximum, well-tolerated dose. A follow up ECG will be performed 1 week after the dose reduction (during an unscheduled Visit) to ensure the QTc is no longer significantly prolonged.
- A complete physical examination will be performed at the time of the initial and final study Visit, as well as during the early termination Visit, if applicable. Any and all changes in the examination happening during the trial will be recorded, and reported when appropriate.
- Vital Signs (including weight) will be measured and recorded during all scheduled study Visits, including the early termination Visit, if such a Visit happens. Any and all gross abnormalities or significant changes will be reported.
- Suicidal thoughts or actions are a possible side effect of AUSTEDO use. The Columbia Suicide
 Severity Rating Scale (C-SSRS) will be administered during all scheduled study Visits, including
 the early termination Visit, if such a Visit happens. Development of suicidality as determined by
 this instrument at any point during the trial will warrant the immediate discontinuation of the
 study drug, as well as psychiatric care as determined necessary by the investigator. Subjects
 with any signs or suicidality during Visit 1 as detected by the scale will be immediately excluded
 from participating in the trial.

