3.5.1.1 Visit 1: Screening (Week 1)

This will be the first study Visit. During this Visit, subjects will sign the informed consent form, their eligibility for study participation will be confirmed, and study drug will be dispensed. Demographic and baseline characteristics (age at screening, gender, weight, height, BMI, race, ethnicity, medical history, physical examination) will be listed for individual subjects. The activities to be performed during Visit 1 include:

- Informed consent
- Medical history will be obtained
- Medication history will be obtained. All prior medications will be assigned a generic name based on the World Health Organization (WHO) Dictionary.
- Concomitant medications will be reviewed (subjects receiving a strong CYP2D6 inhibitor will be
 instructed to titrate up to 36 mg during the ramp-up period, not to 48 mg, once study drug is
 dispensed). All concomitant medications will be assigned a generic name based on the World
 Health Organization (WHO) Dictionary. When applicable, date of last and next botulinum toxin
 injections will be recorded, as well as the date of the last DBS setting changes.
- Complete physical exam
- Vital signs
- 12-lead ECG
- C-SSRS
- SSS
- MMSE
- First video of the movement disorder examination

- MDS-UPDRS Part III
- Revision of eligibility criteria (inclusion/exclusion criteria will be reviewed)
- Dispense study drug (if eligible for participation)

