3.5.1.4 Visit 4: Maintenance dose ends

Visit 4 will happen during the last week of the maintenance period: during week 12 for subjects on 48 mg/day of AUSTEDO, during week 10 for those subjects receiving a strong CYP2D6 inhibitor, and 6 weeks after the initiation of the maintenance period for subjects who experienced dose-limiting side effects during the ramp-up period. This will be the last visit while on study drug, and at this time

subjects will be instructed on when to stop AUSTEDO. According to the package insert,³ treatment with AUSTEDO can be discontinued without tapering. The activities to be performed during Visit 4 include:

- Adverse events will be assessed
- Vital signs
- 12-lead ECG
- C-SSRS
- SSS
- MMSE
- Second video of the movement disorder examination
- MDS-UPDRS Part III
- Patient Global Impression of Improvement
- 3.5.1.5 Visit 5: Post treatment evaluation

Visit 5 will be scheduled 1 week (or up to 9 days, if necessary) after study drug cessation. This is a safety Visit. The activities to be performed during Visit 5 include:

- Adverse events will be assessed
- Complete physical exam
- Vital signs
- 12-lead ECG
- C-SSRS
- SSS
- Returned bottles will be collected and compliance will be assessed
- 3.5.2 Special situations that could cause changes in Study Visit Schedule
- 3.5.2.1 Shortened Ramp-up Period

There are three scenarios that could shorten the duration of the ramp-up period:

- 1. Study subjects taking a strong CYP2D6 inhibitor: The maximum dose of AUSTEDO allowed for subjects taking a strong CYP2D6 inhibitor will be 36 mg/day. These study subjects will start AUSTEDO at 12 mg/day and increase at weekly intervals in increments of 6 mg per day up to 36 mg/day, if tolerated, as instructed in the package insert.³ For these subjects, the maximum length of the ramp-up period will be 4 weeks.

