3.6.1.3 Physical Examination

A complete physical and neurologic examination will be performed at the time of the initial and final study Visit, as well as during the early termination Visit, if applicable. Abnormalities in the examination appreciated during Visit 1 and reflective of the subject's known dystonia will be recorded and labeled as non-clinically significant. Any and all changes in the examination happening during the course of the trial will be recorded and reported, when appropriate. Figure 2 below shows the form that will capture this data.

	Figure 2	
Date: DD – MMM – YYYY		Study subject number:

Visit Number (circle one): 15 Early termination Visit

The AUDYT Trial Physical Exam Form

Vital signs	s: BP:  / 	WT:lbs
General examination		
Skin:	Normal Abnormal – CS Abnormal – NCS	If abnormal, describe:
Cardiovascular:	Normal Abnormal – CS Abnormal – NCS	If abnormal, describe:
Respiratory:	Normal Abnormal – CS Abnormal – NCS	If abnormal, describe:
Abdomen:	Normal Abnormal – CS Abnormal – NCS	If abnormal, describe:
Extremities:	Normal Abnormal – CS Abnormal – NCS	If abnormal, describe:
Neurologic examination Mental Status:	Normal Abnormal – CS Abnormal – NCS	If abnormal, describe:
Cranial Nerves:	Normal Abnormal – CS Abnormal – NCS	If abnormal, describe:
	Normal Abnormal – CS Abnormal – NCS	If abnormal, describe:
Cerebellar:	Normal Abnormal – CS Abnormal – NCS	If abnormal, describe:
Reflexes:	Normal Abnormal – CS Abnormal – NCS	If abnormal, describe:

Gait:	Normal	If abnormal, describe:
	Abnormal – CS	
	Abnormal – NCS	

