4.1.4 Pharmacokinetics

As stated in the drug's package insert,³ after oral dosing up to 25 mg, plasma concentrations of AUSTEDO are generally below the limit of detection because of the extensive hepatic metabolism of AUSTEDO to the active deuterated dihydro metabolites (HTBZ), α -HTBZ and β -HTBZ. Linear dose dependence of Cmax and AUC was observed for the active metabolites following single or multiple doses of AUSTEDO (6 mg to 24 mg and 7.5 mg twice daily to 22.5 mg twice daily).

Absorption

Following oral administration of AUSTEDO, the extent of absorption is at least 80%. Plasma concentrations of AUSTEDO are generally below the limit of detection after oral dosing. Peak plasma concentrations (Cmax) of deuterated α -HTBZ and β -HTBZ are reached within 3 to 4 hours after dosing.

Effect of Food

The effects of food on the bioavailability of AUSTEDO were studied in subjects administered a single dose with and without food. Food had no effect on the area under the plasma concentration-time curve (AUC) of α -HTBZ or β -HTBZ, although Cmax was increased by approximately 50% in the presence of food.

Distribution

The median volume of distribution (Vc/F) of the α -HTBZ, and the β -HTBZ metabolites of AUSTEDO are approximately 500 L and 730 L, respectively. Results of PET-scan studies in humans show that following intravenous injection of 11C-labeled tetrabenazine or α -HTBZ, radioactivity is rapidly distributed to the brain, with the highest binding in the striatum and lowest binding in the cortex. The in vitro protein binding of tetrabenazine, α -HTBZ, and β -HTBZ was examined in human plasma for concentrations ranging from 50 to 200 ng/mL. Tetrabenazine binding ranged from 82% to 85%, α -HTBZ binding ranged from 60% to 68%, and β -HTBZ binding ranged from 59% to 63%.

Elimination

AUSTEDO is primarily renally eliminated in the form of metabolites. The half-life of total ($\alpha+\beta$)-HTBZ from AUSTEDO is approximately 9 to 10 hours. The median clearance values (CL/F) of the α -HTBZ, and the β -HTBZ metabolites of AUSTEDO are approximately 47 L/hour and 70 L/hour, respectively, in the Huntington's disease patient population.

Metabolism

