11. APPENDICES

11.1 Appendix 1: Subject Visit schedule

	Screening	Dosing			Visit 5	Early termination
	Visit 1	Visit 2	Visit 3	Visit 4		Visit
Visit	Ramp-up starts		Maintanance starts	Maintanance ends	Post treatment	
Informed consent	X					
Eligibility Criteria	X					
Medical History	X					
Medication History	X					
Collect/review Adverse Events and Con Meds	X	X	X	X	X	X
Complete Physical Exam	X				X	X
Vital signs	X	X	X	X	X	X
12-lead ECG	X	X	X	X	X	X
CSSRS	X	X	X	X	X	X
Epworth Sleepiness Scale	X	X	X	X	X	X
MMSE	X			X		X
Video	X			X		X
MDS-UPDRS Part III	X			X		X
Patient Global Impression of Improvement				X		X
Dispense Study Drug (bottles)	X					
Collect returned bottles & assess compliance					X	X

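### No completer has the complete physical and neurologic examination on drug, so it can miss signs that reverse after stopping

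*Combined protocol and SAP*

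**What the plan says.** Section 2.3 includes the complete physical examination in its list of assessments for safety and tolerability, which is the primary objective (section 2.1): "A complete physical examination will be performed at the time of the initial and final study Visit". Section 3.6.1.3 makes the content explicit: "A complete physical and neurologic examination will be performed at the time of the initial and final study Visit", with early termination added.

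The other places agree:
- The Visit 1 list (section 3.5.1.1) has the examination, with dispensing of study drug as its last item.
- The lists for Visits 2, 3 and 4 do not have it. Visit 4 is described as the last visit on drug.
- The Visit 5 list (section 3.5.1.5) has it, and the timing is "Visit 5 will be scheduled 1 week (or up to 9 days, if necessary) after study drug cessation".
- The Figure 2 form offers Visits 1 and 5 and early termination.
- The "Complete Physical Exam" row of Appendix 1 is marked for Visit 1, Visit 5 and early termination only.

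Section 4.1.4 says that the half-life of the total active metabolites "is approximately 9 to 10 hours". Section 1.2.2 reports that, one week after stopping in the Huntington's chorea trial, "the Total Maximal Chorea Scores of subjects who had received AUSTEDO returned to baseline".

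**The concern.** The protocol promises to record any change in the examination during the trial. For a completer, however, the only repeat examination comes after washout. A sign that appears on treatment and resolves within a week of stopping would not be found by this assessment. The same protocol times the MMSE and the MDS-UPDRS Part III to Visit 4, where on-drug signs can be seen, and gives no reason for treating this examination differently.

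What is at stake is how a clean result reads. An unchanged examination could be taken as on-treatment reassurance, although it was made with almost no drug on board. Section 6.1.1 summarises all safety data from the first dose onward and does not separate examinations made on drug from those made after stopping.

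**Working it through.** **Timeline.** The plan's own durations reproduce: 6 weeks ramp-up + 6 maintenance + 1 washout = 13 weeks, and 4 + 6 + 1 = 11 weeks with a strong CYP2D6 inhibitor. Tables 3 and 4 give zero tablets in weeks 13 and 11. Visit 5 is therefore an off-drug visit on either schedule, and scheduled complete examinations on drug for a completer are 0 of 2.

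**Exposure at Visit 5.** Half-lives elapsed = 24 × days ÷ half-life in hours; fraction remaining = 0.5 to that power. Days come from section 3.5.1.5, half-life from section 4.1.4.

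| Days off drug | Half-life (h) | Half-lives elapsed | Remaining |
|---|---|---|---|
| 7 | 9 | 18.7 | 0.00024% |
| 7 | 10 | 16.8 | 0.00088% |
| 9 | 9 | 24.0 | 0.000006% |
| 9 | 10 | 21.6 | 0.00003% |

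**Strong CYP2D6 inhibitors.** Section 4.8 gives about 3-fold exposure to the active metabolites but no half-life. If, as an assumption, the half-life also triples to 27 to 30 h, then 7 days is 6.2 to 5.6 half-lives (1.3% to 2.1% remaining) and 9 days is 8.0 to 7.2 (0.4% to 0.7%). That is still small, but well above the table.

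**Effect at one week off drug.** Low exposure is not the same as no effect. The two background studies in section 1.2.2 differ. Chorea scores were back at baseline. In the open-label tic study the score had fallen 11.6 points and then rose 5.6, so 5.6 ÷ 11.6 = 48% of the change was lost and 6.0 ÷ 11.6 = 52% remained. That study had no control group, so part of the remainder may not be drug effect.

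**Early termination.** After a QTc stop the visit is due within 3 business days (section 5.6), which can span 5 calendar days. At the stated half-life, 15.7% to 18.9% remains after 1 day, 0.39% to 0.68% after 3 and 0.010% to 0.024% after 5. The off-drug interval therefore varies among early leavers and differs from that of completers.

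**What Visit 4 already covers, against the Figure 2 form.**
- Mental status: MMSE, in part.
- Motor function and gait: MDS-UPDRS Part III and the video tasks.
- Coordination: finger-to-nose and tandem walking on video.
- Cranial nerves: in part, through speech, facial expression, eye closure, tongue and jaw tasks.
- Cardiovascular: ECG and vital signs, also at Visits 2 and 3.
- Skin, respiratory, abdomen, extremities and reflexes: no dedicated scheduled on-drug assessment.

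**The case against.** The schedule is consistent throughout, and section 1.3.1 gives the off-drug visit a purpose: a final safety evaluation one week after stopping. As an exit examination it is sensible. The physical examination is not named among the endpoints in section 3.7.1.2, and no test of it is planned. Adverse events are asked about at every visit, investigators report what they directly observe, and unscheduled visits are allowed. All of this stands, and it keeps the point small.

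It does not close the gap. The adverse event question is nonspecific and relies on the subject noticing something. Unscheduled visits do not require the examination. The video is an efficacy tool whose raters are told to score dystonia alone. The exit purpose also does not explain why two other safety examinations are placed at Visit 4 and this one is not.

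A reader might infer that the examination cannot show a drug effect at all, or that on-drug neurologic safety goes unexamined. The documents support neither. A change from Visit 1 to Visit 5 can reflect a persistent, slowly resolving or withdrawal effect, as the tic study illustrates, and the Visit 4 tools reach most neurologic domains. Nor do the documents show that an unchanged Visit 5 examination will be presented as on-treatment evidence; that is a risk in reporting, not a stated plan.

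**Conclusion.** The point holds as a limited design weakness. For every completer, a listed safety assessment is made only before the drug and 7 to 9 days after it. It is suited to finding lasting or post-withdrawal change and poorly suited to finding reversible on-drug signs. The uncovered part is mainly skin, chest, abdomen, extremities, reflexes and some cranial nerve items.

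The figure of about 17 to 24 half-lives rests on the stated 9 to 10 h applying to the subject; with a strong CYP2D6 inhibitor it may be fewer. The conclusion about timing does not depend on that figure, because no on-drug examination is scheduled in any case. No endpoint or analysis changes, and the sections do not contradict one another.

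**What to change.** Perform the complete physical and neurologic examination at Visit 4. At Visit 5, repeat the systems that changed at Visit 4 or for which the subject reports a new problem. Amend sections 2.3, 3.5.1.4, 3.5.1.5 and 3.6.1.3, the visit numbers on Figure 2 and the Appendix 1 row. Keep Visit 5 on Figure 2, because that form also carries the visit's vital signs (Figure 3 lists only Visits 2, 3 and 4). Report Visit 1 to Visit 4 as the on-drug comparison, and report examinations made after stopping, including those at early termination, separately with the days since last dose.

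The cost is protocol wording and one form; the complete examination is moved to a visit that already takes place. The small downside is that a subject with an unchanged Visit 4 examination and no new problem has no complete off-drug examination. If that is unwelcome, keeping Visit 5 in full and adding Visit 4 costs at most 15 further examinations. The least that would help is a sentence saying that the Visit 5 examination detects only persistent or post-withdrawal change.

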2.4 Efficacy Outcome Assessments

Although the AUDYT trial is not powered to accurately establish efficacy of AUSTEDO, the following assessments will be performed:

- Patient Global Impression of Improvement: During Visit 4, subjects will be asked to rate the change in their dystonic symptoms using this Scale.
- Clinical Global Impression of Improvement Scale: A video will be made of each subject's movement disorder examination during Visits 1 and 4. Videos will be sent to raters blinded to Visit number and recording date. Raters will be asked to compare the videos looking for any change in the subjects' dystonic symptoms. Their impressions will be recorded using this Scale.
- Global Dystonia Rating Scale: Blinded video raters will also be asked to rate the severity of the subjects' dystonia in all videos using this Scale.

3. STUDY METHODS

3.1 Study Design

This is a single-center, open-label study of AUSTEDO in study subjects with dystonia. The study will provide preliminary experience of the safety, tolerability, and clinical activity of AUSTEDO in study subjects with dystonia. Study duration will be up to 13 weeks from screening (Visit 1) to the post treatment evaluation (Visit 5) for study subjects able to titrate up to 48 mg/day. Treatment period from drug initiation to final on-treatment Visit will be 12 weeks, or less, as follows: during the ramp-up period, study drug will start at 12 mg/day (6 mg twice daily) and will be titrated weekly by 6 mg/day increments until either 1) the maximal allowable dose (48 mg/day) is reached, or 2) dose-limiting sideeffects occur. Dose-limiting toxicity will be defined in this protocol as the development of any of the following during the titration period: a) new or worsening depression, b) worsening of dystonic symptoms, c) QTc increase of >39 but <60 milliseconds from baseline, or d) any other sign or symptom that, at the PI's discretion, would preclude further safe titration of the study drug. In study subjects receiving a strong CYP2D6 inhibitor, the maximum allowed dose of AUSTEDO will be 36 mg/day, reducing study duration to 11 weeks (given a shortening in the ramp-up period). Study subjects who experience dose-limiting side effects will be maintained on their maximum tolerated dose. Once the maximal dose is established for each participant, they will complete 6 continuous weeks on this dose (maintenance period), followed by a 1-week washout. For study subjects unable to titrate up to 48 mg/day due to side effects, the 6 weeks of maintenance will start once they reduce the study drug to the maximum dose they can tolerate well.

Adverse events will be monitored throughout the study and will be reported after drug initiation. Dose reductions, suspensions, and withdrawals due to adverse events will be recorded. ECG readings, the Columbia Suicide Severity Rating Scale and the Stanford Sleepiness Scale will be assessed at all scheduled study Visits. The Mini Mental (MMSE) Scale will be performed at screening and at the final on-treatment Visit (Visit 4, usually during week 12). A video examination of the study subjects will be made at screening (right before initiation of the study drug), and after 6 weeks on AUSTEDO at a steady dose (right before drug cessation). Part III of the MDS-UPDRS will be performed at both of these Visits as well to screen for the appearance of drug-induced parkinsonism. Videos will be sent to raters blinded to Visit number and recording date, who will assess changes in the subjects' dystonic symptoms. Patients will be contacted on a weekly basis via telephone during the ramp-up.

